## Clinical Investigation Plan

### 6.2.1 Baseline Clinical Assessments

The following data will be recorded at baseline:

- Subject demographics
- Occupational and lifestyle information
- Subject medical history (pain history and other interventions for pain management)
- Subject pain diagnosis and pain location
- NRS score
- EQ-5D-5L
- PROMIS-29
- Opioid medication usage
- ODI (only for subjects with back pain)
- NDI (only for subjects with neck pain)
- WOMAC index score (only for subjects with knee and hip pain)
- Serious adverse events resulting in death (if applicable)

### 6.3 Radiofrequency ablation procedure(s)

#### 6.3.1 Procedures Involved in the Use of the Device Under Investigation

The RFA procedure(s) will be conducted within 30 days of baseline and according to minimal requirements for different patient populations as outlined in the guidance document “Practice Guidelines for RFA procedures in the ROSTRA study”.

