## 4.0 ENDPOINTS

### 4.1 Primary Effectiveness and Safety Endpoint

The primary effectiveness endpoint is the relative change in Numeric Rating Scale (NRS) [REDACTED] [REDACTED] follow-up visit. NRS is the patient's self-rating of average pain intensity for the area being treated over [REDACTED] from 0 "no pain" to 10 "worst pain imaginable". This will be calculated for each represented indication.

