### 4.2 Descriptive Endpoints

The following descriptive endpoints will be reported using summary statistics.

1. The following will be characterized at RFA procedure(s):
  - Overall procedure and RF time
  - A summary of Abbott RFA accessory model numbers used in the procedure
2. The following will be characterized at follow-up visits:
  - Patient reported (%) pain relief
  - Patient satisfaction
  - Patient Global Impression of Change (PGIC): to evaluate the subject's impression of change in his/her condition since the beginning of the study treatment
  - Device- and procedure-related adverse events
  - Device deficiencies
3. Change from baseline to each follow-up visit in
  - NRS (raw change); the raw change is defined as (Baseline NRS score – Follow-up NRS score)
  - EQ-5D quality of life survey, consisting of a descriptive system and the EQ VAS. The descriptive system comprises five dimensions: mobility, self-care, usual activities, pain/discomfort, and anxiety/depression. The EQ VAS records the patient's self-rated health on a vertical visual analogue scale
  - PROMIS-29 assesses pain intensity using a single 0-10 numeric rating item and eight health domains (physical function, fatigue, pain interference, depressive symptoms, anxiety, ability to participate in social roles and activities, cognitive function/abilities, and sleep disturbance) using four items per domain
  - Opioid medication usage
  - Oswestry Disability Index (ODI): 10-item scale that evaluates disability related to low-back pain (only for back pain patients)
  - Neck Disability index (NDI): 10-item scale that evaluates disability related to neck pain (only for neck pain patients)
  - The Western Ontario and McMaster Universities Osteoarthritis Index (WOMAC) index score: measures pain, stiffness, and functional limitations (only for knee and hip pain patients)
4. Relative change in NRS [REDACTED]
5. Responder analysis [REDACTED]
  - Proportion of subjects with  $\geq 30\%$  decrease on NRS
  - Proportion of subjects with  $\geq 50\%$  decrease on NRS

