### 5.3.1 All candidate subjects

#### 5.3.1.1 Inclusion Criteria

1. Subject must provide written informed consent prior to any clinical investigation-related procedure
2. Subject is  $\geq$  18 years of age
3. Subject has chronic pain  $>$  6 months and was unresponsive to conservative management
4. Subject has pain on an NRS scale of  $\geq$  6
5. Subject is scheduled for an RFA procedure with the IonicRF generator within 30 days of baseline to treat chronic pain at one anatomical region
6. Subject has stable chronic pain medication use for 30 days

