#### 6.2 Baseline

Baseline assessments should be completed on the same day of enrollment and after the diagnostic block(s) and/or other evaluations to determine if a subject qualifies for an RFA procedure. The diagnostic block should only be used as a diagnostic tool and its therapeutic effect should be completely nullified at the time of the baseline assessment.

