#### 6.3.2 Treatment Procedures

The following information will be collected at (each) RFA procedure:

- Procedure information (e.g., treated vertebral segments, setting, temperature, impedance, voltage)
- Overall procedure and RF time
- X-ray or ultrasound image (documentation of cannula placement)
- A summary of Abbott RFA accessory model numbers used in the procedure
- Device deficiencies (if applicable)
- Serious adverse events resulting in death (if applicable)
- Device- and procedure-related serious adverse events (if applicable)
- Device- and procedure-related adverse events (if applicable)

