## 6.5 Unscheduled Visit

An unscheduled visit is defined as a visit that occurs between the RFA procedure and any of the required follow up visits, except for routine medication visits (as applicable). Data regarding opioid usage, NRS, and adverse events should be documented by completing the appropriate question/CRF as applicable. Any additional CRF, not specified above, may be collected if deemed appropriate by the investigator.

Following an Unscheduled visit, the subject should be seen for the next scheduled study visit within window.

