## Clinical Investigation Plan

### 6.5.1 Schedule of Events

CIP Activity	Enrollment	Baseline	RFA procedure visit(s)	Follow-up visit 3 months (±30 days)	Follow-up visit 6 months (± 30 days)	Unscheduled
Informed Consent	X					
Eligibility	X					
Demographics		X				
Occupational and lifestyle information		X		X	X	
Medical History		X				
Pain diagnosis and pain location		X				
Opioid Medication		X		X	X	X
NRS		X		X	X	X
EQ-5D-5L		X		X	X	
PROMIS-29		X		X	X	
ODI*		X		X	X	
NDI*		X		X	X	
WOMAC index score*		X		X	X	
Device information			X			
Procedure Information and time				X		
X-ray or ultrasound image				X		
Patient reported pain relief					X	X
PGIC					X	X
Patient satisfaction					X	X
New area of chronic pain					(X)	(X)
Device deficiencies			(X)			
Protocol deviation		(X)	(X)	(X)	(X)	(X)
Serious adverse events resulting in death	(X)	(X)	(X)	(X)	(X)	(X)
Device- and procedure-related SAEs			(X)	(X)	(X)	(X)
Device- and procedure-related AEs			(X)	(X)	(X)	(X)
Withdrawal			(X)	(X)	(X)	(X)

(X) if applicable

\*For specific indications only

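### No pain score is scheduled between the enrolment-day baseline and an RFA up to 30 days later, so pre-treatment change in NRS is included in the RFA effect and cannot be quantified

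*Protocol*

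**What the plan says.** - **Timing.** Protocol 6.2: "Baseline assessments should be completed on the same day of enrollment". Inclusion criterion 5 in 5.3.1.1: "Subject is scheduled for an RFA procedure with the IonicRF generator within 30 days of baseline". Section 6.3.1 repeats the limit: "The RFA procedure(s) will be conducted within 30 days of baseline".
- **Data at the procedure.** Section 6.3.2 begins "The following information will be collected at (each) RFA procedure" and lists procedure settings and times, imaging, accessory models, device deficiencies and safety events. It has no pain score and no medication item. In 6.5.1, NRS and opioid medication are marked at baseline, 3 months, 6 months and unscheduled visits, but not at the RFA visit.
- **Unscheduled visits.** These do record NRS and opioid use, but 6.5 places them after treatment: "An unscheduled visit is defined as a visit that occurs between the RFA procedure and any of the required follow up visits".
- **Reference value.** In 4.2, "the raw change is defined as (Baseline NRS score – Follow-up NRS score"). The reference for the primary relative change is redacted in 4.1, but baseline is the only NRS scheduled before RFA.
- **Design.** Single arm (3.0); entry at NRS of 6 or more (5.3.1.1); NRS is one question about the past 24 hours (6.4.2.1); about 20 subjects per indication (5.1). The hypothesis is two-sided against zero at the 5% level (8.2.1), by indication and without multiplicity adjustment (SAP 2.10).
- **Medication.** Use must be stable for 30 days at entry (5.3.1.1). Limiting increases from baseline to the primary endpoint is recommended, at the investigator's discretion (3.0). Follow-up records opioid use when the dosage has changed (6.4.1).

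**The concern.** With no control arm, the effect estimate is a before-and-after difference, so whatever happens between the baseline reading and the procedure becomes part of it. Two things can happen in that interval. Subjects selected on a single reading of 6 or more will tend to score lower when asked again, even if nothing has changed; that regression to the mean favours RFA. Pain may also truly rise or fall while the subject waits, in either direction.

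Because the null value is zero and SAP 2.7 ties success to meeting the primary endpoint, any mean fall before RFA counts towards success. A reading just before the procedure would show how large this component is. It cannot be recovered afterwards.

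**Working it through.** The plan states no figure for pre-treatment drift, and its sample-size text is redacted, so there is no figure of its own to reproduce. The first step is a reading of the documents. The rest is illustration on assumptions that are named.

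**1. Is pain measured during the wait?**

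| Contact | NRS | Opioid use | Source |
|---|---|---|---|
| Baseline (enrolment day) | yes | yes | 6.2, 6.2.1, 6.5.1 |
| Wait, up to 30 days | none scheduled | none scheduled | 6.5 (unscheduled visits start after RFA) |
| RFA visit | no | no | 6.3.2, 6.5.1 |
| 3 and 6 months | yes | if dosage changed | 6.4.1, 6.5.1 |

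The visit list and the schedule agree, so a broken table does not explain the gap.

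**2. How much of the interval is it?** Taking 3 months as 91 days and 6 months as 183 days, and a full 30-day wait: 30/(30 + 91) = 25% of the baseline-to-3-month interval and 30/(30 + 183) = 14% of the baseline-to-6-month interval. With the ±30-day windows the ranges are 20% to 33% and 12% to 16%.

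**3. What is a drift worth on the relative scale?** Let d be the fall before RFA and B the baseline; the share of baseline is d/B. For d = 0.5: 0.5/10 = 5.0% to 0.5/6 = 8.3% over all eligible baselines. For d = 1: 10.0% to 16.7%. The values of d are assumed.

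**4. How far would the estimate move if re-based?** Let P = B − d be the pre-procedure score and F the follow-up score. The difference between (B − F)/B and (P − F)/P is F·d/(B·P).
- Pain halves, B = 7, F = 3.5, P = 6.5: 50.0% against 46.2%, a shift of 3.8 points.
- Pain halves, B = 8, F = 4, P = 7.5: 50.0% against 46.7%, a shift of 3.3 points.
- With d = 1 in the same two cases: 8.3 and 7.1 points.
- No change after RFA (F = P): the shift is d/B, the full amount in step 3.

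**5. Responder status.** F = 5 is a 37.5% decrease from 8 but 28.6% from 7, which crosses the 30% cut. F = 4 is 50% from 8 but 42.9% from 7, which crosses the 50% cut.

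**6. Regression to the mean alone.** A simulation with no treatment effect assumed an unselected NRS mean of 6 to 7, SD 1.5 to 2, test-retest correlation 0.6 to 0.9, independent reading errors, and selection on the baseline reading itself. Measured from that reading, the apparent fall was 0.06 to 0.54 points (0.5% to 6.5% relative). An assumed two-sided one-sample t-test of relative change at n = 20 rejected 5.8% to 22.7% of the time instead of 5%. Measured from a second pre-treatment reading, the mean raw change was about 0 and the raw-change test rejected 4.8% to 5.3% of the time.

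**7. Set against precision.** At n = 20 the 95% half-width is 2.093 × SD/√20: 14.0 points for an assumed SD of 30, and 18.7 for 40. A drift of 5 points alone would reject zero with probability 0.19, 0.11 or 0.08 for SDs of 20, 30 or 40; a drift of 10 points, with probability 0.57, 0.29 or 0.19.

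**The case against.** An enrolment-day baseline with treatment capped at 30 days is a defensible choice for a real-world post-market study. Two single 24-hour readings in about 20 subjects mix drift with measurement error, and procedure-day anxiety may affect the second. A 0.5-point drift lies well inside the sampling uncertainty of one indication. All of this stands. It is why the added reading should not replace the baseline, and why this is an improvement rather than a fatal flaw. It does not remove the point: regression to the mean is systematic, has a known direction, and does not shrink as numbers grow.

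A reader might infer more than the documents support:

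- **That wearing-off of the diagnostic block flatters RFA.** Protocol 6.2 requires the block's effect to be gone at baseline. If some remained, its loss would raise pain before RFA and understate the benefit.
- **That medication changes during the wait go unseen.** An opioid dosage change that persists should be reported at follow-up as a change from baseline. What remains is narrower: the visible text does not date such changes relative to RFA (the CRFs are held separately), and non-opioid analgesic changes are not listed for collection.
- **That a procedure after day 30 is unregulated.** It would depart from 6.3.1, be reportable under 10.5, and be summarised under SAP 3.4. The visible text has no repeat baseline, but the analysis-set definitions are redacted, so how late procedures are analysed cannot be seen.
- **That a pre-procedure score would supply the missing control.** Subjects continue their usual medication during the wait, and at most 30 days before treatment is not a comparator for 3- and 6-month outcomes. Natural course and placebo response after RFA would still be counted as effect.

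**Conclusion.** The point holds. No NRS is scheduled between the enrolment-day baseline and RFA, so regression to the mean and other pre-RFA pain change are part of the estimated effect and cannot be quantified. The net bias may run either way, although the regression component favours RFA. Medication is the lesser part.

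The size cannot be derived from the documents. For an assumed 0.5-point drift it is 5.0 to 8.3 percentage points of baseline across NRS 10 to 6. Re-basing would shift the estimate by about 3 to 4 points if pain halves from 7 or 8, and by up to the full amount if pain does not change after RFA. The rejection rates in the working depend on assumed SDs, correlations and test, so they show that the mechanism can matter, not that it does here. Nothing in the documents shows that the RFA effect will be mainly artefact. The change is worth making because it is cheap and the reading is lost once the procedure is done.

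**What to change.** - **Protocol 6.3.2 and 6.5.1:** at the first RFA visit, before any sedation or anaesthetic, ask the existing one-item NRS and a yes/no question on whether any analgesic has changed since baseline.
- **SAP:** keep the enrolment baseline as the primary reference. Report the baseline-to-pre-procedure change by indication, and repeat the primary and responder analyses with the pre-procedure NRS as a sensitivity baseline. State how far the conclusions depend on the choice.
- **SAP detail:** the pre-procedure score has no floor of 6. Relative change is undefined at 0 and unstable at low scores, so give a rule for these and show raw change alongside.

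The cost is two questions at a visit that already takes place and one sensitivity table. The downside is procedure-day anxiety and single-reading noise, so the new score should serve for sensitivity only. The report should say that it isolates the wait and entry-selection regression, and nothing after RFA.

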#### 6.3.2 Treatment Procedures

The following information will be collected at (each) RFA procedure:

- Procedure information (e.g., treated vertebral segments, setting, temperature, impedance, voltage)
- Overall procedure and RF time
- X-ray or ultrasound image (documentation of cannula placement)
- A summary of Abbott RFA accessory model numbers used in the procedure
- Device deficiencies (if applicable)
- Serious adverse events resulting in death (if applicable)
- Device- and procedure-related serious adverse events (if applicable)
- Device- and procedure-related adverse events (if applicable)

### 6.4 Follow-up Assessments

#### 6.4.1 Follow-up for All Subjects

Follow-up visits will occur at 3 and 6 months ( $\pm$  30 days) after the (last) RFA procedure.

The following data will be collected at each visit:

- Occupational and lifestyle information
- NRS score

## Clinical Investigation Plan

- EQ-5D-5L
- PROMIS-29
- Opioid medication usage (only if there is a change in dosage from baseline or previous study visit)
- Patient reported (%) pain relief
- Patient satisfaction
- PGIC
- New area of chronic pain (if applicable)
- ODI (only for subjects with back pain)
- NDI (only for subjects with neck pain)
- WOMAC index score (only for subjects with knee and hip pain)
- Serious adverse events resulting in death (if applicable)
- Procedure-related serious adverse events (if applicable)
- Procedure-related adverse events (if applicable)

### 6.4.2 Patient Reported Outcome (PRO) Measures

The Investigator, Coordinator or site designee will administer the PRO questionnaires via paper for later transcription to EDC, or electronically. If the subject reported outcome questionnaire is provided to the subject electronically, the source data will be available in the EDC system for the site's records. It is important the subject understands the meaning of all words and instructions in the questionnaires. The subject should be instructed to ask any questions about the questionnaires if further explanation is needed. Once the questionnaires are completed, the Coordinator or designee will review for completeness to verify that all questions have been answered according to the directions provided.

Alternatively, if the subject is unable to attend a follow up visit in person, questionnaires may be sent to the subject and returned to the site. The Coordinator or designee should schedule a call with the subject to clearly explain the questionnaires and answer any questions the subject may have. A second alternative if the subject is unable to attend a follow up visit in person is that the Investigator or designee may schedule a phone call or telemedicine visit with the subject to review the questionnaires. The Coordinator or designee should document the subject's responses on the worksheet, note that the responses were collected via phone or video call, save that document as source data, and enter the information in the EDC system.

#### 6.4.2.1 Numerical Rating Scale (NRS)

All subjects should answer the NRS question. The pain NRS consists of 1 question that will be asked by interviewing the subjects. Patients will be asked to rate, from 0 (no pain) to 10 (worst imaginable pain), their average pain over the past 24 hours specific to the area(s) of chronic pain being treated. A higher score indicates greater pain intensity.

#### 6.4.2.2 EuroQol-5 Dimensions (EQ-5D)

All subjects should complete the EQ-5D questionnaire. EQ-5D is a standardized instrument for use as a measure of health outcome applicable to a wide range of health conditions and treatments. It provides a simple descriptive profile and a single index value for health status. The EQ-5D-5L descriptive system comprises the following 5 dimensions: mobility, self-care, usual activities, pain/discomfort, and anxiety/depression. Each dimension has 5 levels: no problems, slight problems, moderate problems, severe problems, and extreme problems. A visual analog

## Clinical Investigation Plan

scale (VAS) for health is also included in the measure as a patient-reported estimate of overall health status.

### 6.4.2.3 PROMIS-29

All subjects should complete the PROMIS-29 questionnaire. The PROMIS-29 is an adult scale developed in partnership with the National Institutes of Health (NIH) to estimate overall quality of life by assessing the following domains known to impact activities of daily living: physical function, sleep disturbance, depression, anxiety, fatigue, pain interference, pain intensity, cognitive function, and social role satisfaction. The scale requires subjects to rate the frequency and/or severity of symptoms and experiences related to each of these domains. A total score is calculated and transformed against normative data into a t score indicating global quality of life in relation to population norms. Subscales are defined by each domain described above and can be examined separately to parse separate symptoms or deficiencies in quality of life. The final item is an 11-point pain intensity numerical rating scale (NRS) by which the subject rates their average pain over the past 7 days. Subjects should read each item and check the one box that most closely represents their response.

### 6.4.2.4 Patient Global Impression of Change (PGIC)

All subjects should answer the PGIC question. The PGIC is a categorical rating scale used to evaluate the subject's impression of change in his/her condition since the beginning of the study treatment. The subject will be requested to rate their overall change in activity limitations, symptoms, emotions and overall quality of life related to his/her condition on a seven-point categorical scale via an interview technique. The categories are as follows: 1 - no change, 2 - almost the same, 3 - a little better, 4 - somewhat better, 5 -moderately better, 6 - better, and 7 - a great deal better. Although this tool does not specify the area of change (e.g., pain, function, quality of life, etc.), it allows for an overall integrated assessment from the prospective of the subject. PGIC values of 6 or 7 are reported to correlate best with actual change.

### 6.4.2.5 Oswestry Disability Index (ODI)

Only subjects with low back disability or buttocks pain should complete the ODI questionnaire. The ODI is an index derived from the Oswestry Low Back Pain Questionnaire used by clinicians and researchers to quantify disability for low back pain. The self-completed questionnaire contains ten topics concerning intensity of pain, lifting, ability to care for oneself, ability to walk, ability to sit, sexual function, ability to stand, social life, sleep quality, and ability to travel. Each topic category is followed by 6 statements describing different potential scenarios in the subject's life relating to the topic. The subject checks the statement which most closely resembles their situation. Each question is scored on a scale of 0–5 with the first statement being zero and indicating the least amount of disability and the last statement is scored 5 indicating most severe disability. The scores for all questions answered are summed, then multiplied by two to obtain the index (range 0 to 100). Zero is equated with no disability and 100 is the maximum disability possible. Five different levels of disability are defined within that range; minimal (0-20%), moderate (21-40%), severe (41-60%), crippling (61-80%), and bed bound or exaggerated symptoms (81-100%). A decrease of 13% or more on the 0-100% scale demonstrates a meaningful, clinical improvement in disability.

## Clinical Investigation Plan

### 6.4.2.6 Neck Disability Index (NDI)

Only subjects with neck pain disability should complete the NDI questionnaire. The NDI is designed to measure neck-specific disability. The questionnaire has 10 items concerning pain and activities of daily living including personal care, lifting, reading, headaches, concentration, work status, driving, sleeping, and recreation. The measure is designed to be given to the patient to complete and can provide useful information for management and prognosis of those with neck pain. Each item is scored out of five (with no disability response given a score of 0) giving a total score for the questionnaire out of 50. Higher scores represent greater disability. The result can be expressed as a percentage (score out of 100) by doubling the total score.

